18.11	Miscellaneous Trial Components	61

PROTOCOL SUMMARY

Study Title	ELIRA-2: Safety and Effectiveness of Transcutaneous Electrical Nerve Stimulation (TENS)-Assisted Weight Loss And/Or Appetite Suppression
Study Coordinating PIs	[name] and [name]
Study Rationale	
Previous studies have shown that TENS facilitates weight loss in overweight subjects. The therapy in these trials was delivered using an over the counter device not optimized for daily use.
 
The present pivotal study will test the hypothesis that daily, wearable TENS is safe and effective for appetite suppression and weight loss therapy in overweight- to Type 1 obese-subjects (i.e. BMI of 25 -35 kg/m² inclusive). Ancillary endpoints include changes in hemoglobin A1c and blood lipids as secondary measures associated with weight loss.

Name of the Device(s) Used in Study	The Elira wearable patch system.
Description of Components	The Elira wearable patch system is an RF coupled, wearable transcutaneous electrical nerve stimulation (TENS) device controlled via Bluetooth by a smart phone unit running a custom application which directs therapy from the patch within safe limits set by a clinician and also includes a diary. Subjects will be supplied as well with paper diaries for appetite and symptoms along with an electronic scale.
Study Design	
Randomized, adaptive parallel arm study. Subjects will be initially screened during a screening period (+/- 7 days). During this screening period, subjects will sign an Informed Consent Form (ICF), have their weight/height and blood pressure measured as part of a physical exam, take a pregnancy test (females of child bearing potential), get blood drawn for analysis (blood lipids, HbA1c), and complete the PHQ-9 and pre-study survey. Subjects will be asked to complete their first batch of diaries to set a baseline hunger value.
 
At the end of the screening period, eligible subjects will be enrolled/randomized in the study and be randomized to either a treatment or control group. After enrolling, both control and treatment subjects will be instructed to follow a healthy diet and reduce calories as desired for the duration of the study and will receive training on the use of the electronic scale and completion of paper diaries. For the treatment group, subjects will be instructed on use of the Elira wearable patch system. Photographs will be taken at the enrollment visit. Following this, subjects will enter the Therapy Period for ~24-weeks.
 
At the 12 week visit, subjects will be assessed for weight loss, blood pressure, blood lipids, HbA1c, patient preference questionnaire and their participation will continue through months 4-6 for the Safety phase of the Therapy Period. The Therapy Period will be considered complete (pending laboratory results, adverse events or serious adverse events). Patient (treatment) photographs will also be taken at the 12 week visit.

Protocol #: CD-005; Version #: 4.0

Original Date: May 8, 2018 Revision Date: May 3, 2019

-Confidential-

	
The study utilizes an adaptive approach where cohorts of enrolled/randomized subjects (in groups of ~25 per arm) are assessed for dose response and progression to achievement of primary and secondary endpoints. Frequent interim endpoint assessment utilizing Markov-chain Monte Carlo (MCMC) methods coupled with Longitudinal analyses will be utilized to determine sample sizes for future cohorts (assessed primarily via Normal dynamic linear modeling [NDLM]). Long term safety of the device will be shown through 6 months of usage.

Subject Population / Sample Size	
The primary endpoints are powered at a final enrollment of 75 subjects per group, for a total of 150 subjects, but interim analyses based on Bayesian posterior probability distributions with multiple imputation will be utilized to assess interim significance.
 
In the event the interim analysis is not significant, up to 300 subjects may need to be enrolled in order to achieve final separation between groups for statistical significance. Thus, Elira may need to screen up to 500 subjects to account for exclusions prior to enrollment.

Study Duration and Sites	
Minimum study duration for each patient will be 25 weeks. As it is expected that recruitment of 150 subjects will take up to 24 weeks, the overall study duration is anticipated to be a minimum of 37 weeks, assuming all cohorts are enrolled. The study will be conducted at up to 10 centers.

Inclusion Criteria	
Subject is between 18 – 65 years of age inclusive.
 
Subject has a BMI of 25-35 kg/ m² inclusive.
 
Subject has signed the informed consent form and is able to comply with study protocol and adhere to study visit schedule.
 
Subject is able to wear and use a wearable, patch TENS system.
 
Subject is able to use a touch screen hand held smart phone.
 
Subject is fluent in English and can complete patient questionnaires.
 
Subject is male or non-pregnant, non-lactating female, who agrees to use effective contraceptive methods throughout the length of the trial based on PI approval.
 
Females of childbearing potential (FOCBP) must have a negative urine pregnancy test at screening or enrollment visit, prior to placement of ELIRA device.

Exclusion Criteria	
Subject has any known gastrointestinal disorder that in the opinion of the PI precludes enrollment into the trial.
 
Subject has had a prior bariatric procedure or any previous procedure on the stomach.
 
Subject has any significant multisystem disease in the opinion of the PI.
 
Subject has > 6.5 HbA1c.
 
Subject has significant cardiac arrhythmia, ectopy, or significant cardiovascular disease.
 
Subject has an existing implanted electrical stimulator (e.g., pacemaker, AICD).
 
Subject is a female of child-bearing potential who is pregnant or intends to become pregnant during the trial period.
 
Subject has current and/or a history of cancer within the past 5 years (not including basal cell carcinoma or cervical carcinoma in situ).

	
Subject has had a weight change of $\pm 5\%$ of his/her Total Body Weight in the 3 months prior to screening.
 
Subject has a moderate / severe psychiatric disorder.
 
Subject has a diagnosed neurological disease.
 
Subject has a diagnosed eating disorder.
 
Subject has a skin disorder affecting the thoracic dermatomes
 
Subject has active or /has ever had shingles in the abdomen area.
 
Subject has abdominal surgery or other scars which may interfere with stimulation in the opinion of the PI.
 
Subject is currently enrolled in other, potentially confounding research.
 
Subject has known allergic reaction to materials in the electrodes and/or is otherwise unable to tolerate stimulation with the wearable TENS system. This includes known allergies to latex, nickel and/or hydrogels.
 
Subject has a history of sensitive skin, including eczema, wheel-and-flare or other skin irritation, per PI discretion.
 
Subject is actively participating or unwilling to discontinue participation in another weight loss program. Subjects may not enroll in paid or unpaid programs that involve in-person or online apps or coaching, beginning new fitness regimens or utilizing meal planning or paid nutritional coaching during the course of the ELIRA study.
 
Subject is taking weight loss control medications including but not limited to OTC medications, Metformin, and Belviq. (See Appendix 8)
 
Subject is planning any major medical treatments or surgeries that could cause weight loss.
 
Subject is unable to take anti-nausea medications planned for the study.
 
Inability to walk at least 0.8 kilometers per day (10 minutes of continuous walking).
 
Current smoker or user of nicotine product or smoking cessation within 1 year of the screening date.
 
History of treatment for or current abuse of drugs or alcohol.
 
A score of ≥ 10 on the Patient Health Questionnaire 9 (PHQ-9), demonstrating moderate depression.
 
Any subject that the investigator considers inappropriate for the study for medical reasons.
 
Subject has a history of moderate/severe migraines or other severe headache disorders requiring the treatment of Topiramate.
 
Subject is on drug therapy which may alter antral motility or appetite, per PI discretion (Appendix 8).

Study Outline
	

	
The diagram illustrates the study timeline. It begins with a grey bar for 'Screening' at -1 week. This is followed by a red bar for 'Enrollment/Randomization' at Day 0. A long blue bar represents the 'Therapy/Control' phase, spanning from Week 1 to Week 20. The 'End of Study' is marked at Week 24. Key visits are indicated by arrows: Screening (Visit 0) at -1 week, Randomization/Enrollment (Visit 1) at Day 0, Therapy (Visits 2-7) at Weeks 1, 4, 8, 12, 16, and 20, and Control (Visits 2-7) at the same weeks. The End of Study (Visit 8) occurs at Week 24.

Dosing Regime
	
Treatment subjects will be trained in rotation of the patch electrodes every 24h such that it is applied to varying locations on the T6/T7 dermatome. Each treatment subject will receive two treatments of up to 40 mA of sustained current stimulation for 30 minutes each delivered approximately 30 minutes prior to meal times (based on established times set in the smartphone application), not to exceed 75min daily without express consent of PI. Based on tolerance of the therapy, a subject may decrease his/her dose by dropping one of the therapy sessions after receiving approval from a clinical coordinator and/or PI. In addition, subjects who do not experience sufficient appetite suppression may also add up to three 5-minute “on-demand” sessions at 20mA between regular doses after receiving approval from a clinical coordinator and/or PI. The nominal stimulation dose per day for any subject will thus be 1200mA (60 minutes at 20 mA) while the maximum dose for any given subject will be 3000 mA (75 minutes at 40 mA).


Visit Schedule
	
Screening/Baseline Visit 0 (-1 week; ± 7 days) – Obtain Informed Consent prior to any study procedures. Confirm subject has met all inclusion criteria and no exclusion criteria. History & Physical including height & weight, diet history, baseline clinical parameters, provide laboratory requisition, urine pregnancy test for women of childbearing potential (FOCBP), and questionnaires. Subjects will be given their first batch of paper diaries to complete to establish a baseline hunger.
 
Enrollment/Randomization Visit 1 (Day 0; ± 7 days) – Confirm subject continues to meet all inclusion criteria and no exclusion criteria. Assessment of T6/T7 dermatomes, clinical parameters, BP, weight, perform urine pregnancy test for FOCBP if not done at screening, administer TFEQ-R18V2 Questionnaire, assess for adverse events and changes to concomitant medications. Subjects will be randomized based on the blocked randomization algorithm.

Treatment and Control subjects will be instructed to follow a healthy diet and reduce calories, if possible, throughout the study and given the Diet Resources sheet in Appendix 18.11. They will also receive an electronic scale with instructions on use will be provided, and 8 copies of a daily paper diary will be provided. Subjects will be instructed to return with their paper diary(ies) at the next scheduled visit.

Only the treatment subjects will receive a handheld smartphone with the custom application and an Elira wearable patch system. It is recommended for treatment subjects to utilize an TENS Clean-Cote Skin Wipes and/or alcohol prep pad wipe to maintain a clean application area for the treatment. Treatment subjects will also receive Cetaphil Moisturizing Lotion to be used nightly after removing the ELIRA patch and applied throughout the abdomen area. Subject will be instructed to notify site immediately if any irritation occurs. Treatment subjects will stimulate under the supervision of the investigator or coordinator for 30 minutes prior to being discharged with the device. Treatment subjects will be assessed for toleration of the stimulation to further evaluate dose adjustment. Treatment subjects will be discharged with the Elira wearable patch system & Smartphone App and instructions on use. Treatment subjects will be instructed to return with the Elira wearable patch system and smartphone app at their next scheduled visit. Completion of patient questionnaires (All subjects). A below the neck photograph of the Treatment subjects will be taken at the enrollment visit, with the subjects dressed in biker shorts and sports bra (F) or athletic shorts (M).

Therapy Phase Visits 2, 3, 4, 5, 6, and 7 (week 1, 4, 8, 12, 16, and 20, respectively; ± 7 days) – Treatment and Control subjects will be assessed for adverse events, changes to concomitant medications and commitment to exclusion criteria. Obtain BP and weight. Administer the TFEQ-R18V2 Questionnaire. Collect and review paper diaries, dispense new paper diaries and review instructions for weekly completion. All subjects will be encouraged to follow a healthy low-calorie diet throughout the study. At week 1, subjects will return their first week’s worth of paper diaries. At week 4, subjects will be given a new set of 8 paper diaries and instructed to complete paper diaries for each week beginning the day after the visit. At week 8, they will return their “week 4 diaries” and be given the next set of 8 paper diaries to be completed each week,....,until the final week of using the device (week 23-24).

Treatment subjects will be assessed for any adverse device effects (ADE), T6/T7 dermatome assessment, review and download of diary data, and stimulation adjustment (if needed). If skin irritation is present, PI will classify as Mild, Moderate or Severe and confirm system compliance (wipes, lotion, patch rotation, etc.). Mild irritation may require up to 3 days without stimulation. Moderate irritation may require up to 2 weeks without stimulation. Severe irritation may require medical attention and study termination. PI or designee will assess when irritation is present and review for resolution. Treatment subjects will be discharged with the smartphone application and the Elira wearable patch system and instructions on use. Treatment subjects will be instructed to return with the Elira wearable patch system and smartphone app at their next scheduled visit. Treatment subjects may be contacted by PI or clinical coordinator periodically through the trial to address any questions or concerns related to device function.

End of Study Visit 8 (week 24; ± 7 days) – Treatment & Control subjects will be assessed for adverse events, changes to concomitant medications and commitment to exclusion criteria. Physical including weight, requisition for laboratory tests, blood

Protocol #: CD-005; Version #: 4.0

Original Date: May 8, 2018 Revision Date: May 3, 2019

-Confidential-

	
pressure, labs, and urine pregnancy test for FOCBP, and completion of questionnaires (– PHQ9, TFEQ-R18V2, and Patient Preference Survey). Collect, and review paper diaries. This visit may be rescheduled if the paper diaries were not completed the week prior.
 
Treatment Group Only- Complete End of Study Questionnaires- subjects will return the Elira wearable patch system and the smartphone application. Treatment subjects will be assessed for ADEs and have their T6/T7 dermatome area examined. Treatment subjects will be photographed (below the neck) in similar attire to their initial visit for weight loss reference.


Study Endpoints
	
Primary Safety/Tolerability Endpoint:
 
Safety/Tolerability will be assessed by the non-inferiority of incidence of serious adverse events (SAEs), unanticipated SAEs(USAEs), device-related SAEs (DSAEs) and Unanticipated Device Related SAEs (UDAEs) that are associated with the TENS therapy throughout the stimulation and the follow-up period versus historical control (compared with other TENS systems).
 
Safety variables will be tabulated and presented for all subjects including enrolled, but discontinued, subjects. Number of subjects undergoing active stimulation and any reasons for discontinuation of study treatment will be tabulated.
 
Safety/Tolerability will be assessed through 6 months of therapy.
 
Primary Effectiveness Endpoint:
 
The primary efficacy endpoint is the percent reduction in appetite suppression as measured by percent change in appetite scores at the end of 3 months of the Therapy period compared to Baseline between Treatment and Control.
 
A co-primary endpoint will be total body weight loss (%TBWL), measured as End Weight – Initial Weight divided by Initial Weight, multiplied by 100, at the end of 3 months of the Therapy period compared to Baseline between Treatment and Control.
 
Secondary Effectiveness Endpoints:
 
Number of subjects reporting >5% total body weight loss at the end of 3 months of the Therapy compared to Baseline between Treatment and Control
 
Blood pressure, blood lipids, and HbA1c at the end of 3 months of the Therapy compared to Baseline between Treatment and Control groups.
 
% changes in BMI at the end of Therapy compared to Baseline between Treatment and Control groups
 
Ancillary Endpoints:
 
Cross validation between smartphone app hunger scales and paper VAS diaries collected at the same times.
 
Changes between the following values:
 
Ease of use/prevalence of use errors associated with the patch unit and dietary application during initial training.
 
Subject preference scores at the end of Therapy compared to Baseline between Treatment and Control groups.


Statistical Analysis
	
Statistical Analysis Plan, 2019MAY31
 
ELIRA -2 Trial: Safety and Effectiveness of Transcutaneous Electrical Nerve Stimulation (TENS)-Assisted Weight Loss and/or Appetite Suppression
 
Protocol Number: CD-005, Original Date:2018MAY08, V4.1, Revised Date:2018AUG14
 
Signature Page
 
Author: [name] _____ Date _____
 
Approver: _____ Date _____
 
Approver: _____ Date _____
 
STATISTICAL CONSIDERATIONS AND ANALYSIS PLAN
 
General Methods
 
Categorical variables will be summarized by number and percent. Continuous variables will be summarized by total number (N), mean, standard deviation (SD), median, minimum and maximum. Ninety-five percent, 2-sided confidence intervals will be reported, as appropriate.
 
As this was a randomized trial, the groups are expected to be balanced on demographic and baseline characteristics. No formal testing for this is planned.
 
Planned analyses and summaries for the primary safety endpoint, co-primary efficacy endpoints, secondary efficacy endpoints and exploratory efficacy endpoints are detailed below.
 
Analysis Populations
 
The intent to treat (ITT) analysis population is defined as all subjects who were enrolled.
 
The modified intent to treat (mITT) analysis population is defined as all subjects who initiated therapy (i.e., initiated their first Treatment Period Visit) and had data through week 12. All safety and effectiveness analyses will be completed on the mITT analysis population.
 
The per protocol (PP) analysis population is defined as all subjects who met all inclusion/exclusion criteria, completed all visits in the study without any major protocol deviations. All effectiveness analyses will be completed on the PP analysis population.

------------------------------------	---

Safety Analyses

The primary safety endpoint is defined as the proportion of subjects free of TENS-related serious adverse events and adverse device effects through the therapy phase, safety success rate. The success rates will be compared between groups using chi-square test or Fisher's exact test, as appropriate.

Efficacy Analyses***Co-Primary Efficacy Analyses***

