6. STUDY ENDPOINTS

6.1 PRIMARY ENDPOINTS

6.1.1 Primary Safety/ Tolerability Endpoints:

- Safety/Tolerability will be assessed by the non-inferiority of incidence of serious adverse events (SAEs), unanticipated SAES (USAEs), device-related SAEs (DSAEs) and Unanticipated Device Related SAEs (UDAEs) that are associated with the TENS therapy throughout the therapy/treatment period versus historical control.
- Safety variables will be tabulated and presented for all subjects including enrolled, but discontinued, subjects. Number of subjects undergoing TENS and any reasons for discontinuation of study treatment will be tabulated.
- Safety variables will be collected over a 6 month duration.

6.1.2 Primary Effectiveness Endpoint:

The primary efficacy endpoint is the percent reduction in appetite suppression as measured by percent change in appetite scores at the end of 3 months of the Therapy period compared to Baseline between Treatment and Control.

A co-primary endpoint will be total body weight loss (%TBWL), measured as $\text{End Weight} - \text{Initial Weight}$ divided by Initial Weight, multiplied by 100, at the end of 3 months of the Therapy period compared to Baseline between Treatment and Control.

6.1.3 Secondary Effectiveness Endpoints:

- Number of subjects reporting >5% total body weight loss at the end of 3 months of the Therapy period as compared to Baseline between Treatment and Control
- Blood pressure, blood lipids, and HbA1c at the end of 3 months of the Therapy Period as compared to Baseline between Treatment and Control groups.
- % changes in BMI at the end of 3 months of the Therapy Period compared to Baseline between Treatment and Control groups.

6.1.4 Ancillary Endpoints:

- Cross validation between smartphone app hunger scales and paper VAS diaries collected at the same times.

Changes between the following values:

- Ease of use/prevalence of use errors associated with the patch unit and dietary application during initial training.
- Subject preference scores at the end of Therapy Period compared to Baseline between Treatment and Control groups.

Protocol #: CD-005; Version #: 4.0

Original Date: May 8, 2018 Revision Date: May 3, 2019

-Confidential-

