To further understand the time points and weekly diary entries on appetite suppression, all time points and weekly entries will be analyzed in a repeated measures analysis of variance (RMANOVA) for each of the four appetite suppression endpoints separately. The RMANOVA will not use percentage changes but will use the actual appetite suppression scores with a factor for group treatment, time (week and time point), as well as the interaction factor between time and treatment.

The occurrence rate for subjects experiencing >5% TBWL at the end of 3 months will be compared between groups using chi-square test or Fisher's exact test, as appropriate.

Blood pressure, blood lipids, and HbA1c at the end of 3 months of the Therapy compared to Baseline between groups using t-tests or Wilcoxon rank sum tests, as appropriate.

The percent change from baseline in BMI at the end of 3 months of the Therapy compared to Baseline between groups using t-tests or Wilcoxon rank sum tests, as appropriate.

Exploratory Efficacy Summaries

Summary statistics will be provided by visit and by group for the other time points (besides the 3 month time point) for percent change from baseline in appetite suppression scores, %TBWL, occurrence rate for >5% TBWL, blood pressure, blood lipids, and HBA1c. In addition, summary statistics will be provided by visit and by group for ease of use, prevalence of use errors associated with patch unit and dietary application, and preference scores.

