8.2 Justification of Sample Size

As per the protocol, the calculation sample size for the study is based on conservative imputation of results from other studies on weight loss including the use of TENS for weight loss. The degree of coaching/dietary support throughout the present study is moderate intensity lifestyle/weight coaching. The sample size modeling assumes an average of 3.5% TBWL in Control Subjects using diet and exercise alone. The estimated weight loss in Treatment Subjects is modeled from preliminary data on T6/T7 dermatomal TENS when used for

weight loss: 6% TBWL. The variance of the responses in the study (i.e. Standard Deviation) was modeled at +/- 5% TBWL. This value was taken from previous dermatomal TENS weight loss study results. The model assumes a 30% drop out rate across groups and an 80% powered endpoint using an adaptive p spending model wherein interim posterior probability assessments are allowed after enrolling proscribe cohorts of not less than 67% of subjects. The alpha penalty will be minimized per interim by assessing the relationship between stimulation (i.e. dose) and weight loss using Normalized Linear Dynamic Modeling (NLDM) to determine overall sample size projected (i.e. futility) rather than assessing the primary hypothesis per se. Monotonicity will not be assumed in this analysis. This modeling provides an estimate of 80 subjects per group, for a total study size of 160 subjects. However, the protocol allows for enrollment of additional subjects should the interim model project under powering of the primary endpoint.

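### The only %TBWL formula is negative for weight loss, the opposite sign to its label, the >5% responder cut-off and the planning values

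*Combined protocol and SAP*

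**What the plan says.** The formula appears twice, in the Protocol Summary (Study Endpoints) and in section 6.1.2, with the same order of subtraction. Section 6.1.2 introduces it with "A co-primary endpoint will be total body weight loss (%TBWL), measured as", and the Summary completes it as "measured as End Weight – Initial Weight divided by Initial Weight, multiplied by 100". No other formula for %TBWL is given.

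The other uses of the term treat loss as a positive quantity:

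- Secondary endpoint, Protocol Summary and section 6.1.3: "Number of subjects reporting >5% total body weight loss at the end of 3 months".
- Secondary analysis, SAP text in the Summary and section 8.1.4: "The occurrence rate for subjects experiencing >5% TBWL at the end of 3 months".
- Sample size, SAP text in the Summary and section 8.2: "The sample size modeling assumes an average of 3.5% TBWL in Control Subjects using diet and exercise alone"; for Treatment, "weight loss: 6% TBWL"; the standard deviation "was modeled at +/- 5% TBWL".

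No sentence takes an absolute value, reverses the sign, or sets a cut-off of -5%.

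**The concern.** A programmer who derives %TBWL from the stated formula gets a variable that falls as weight loss increases. The section 8.1.4 analysis then applies a cut-off of >5% to a variable of that name. Taken mechanically, the two steps flag people who gained more than 5% of their weight and miss everyone who lost weight. The responder rate is a named secondary endpoint and is also to be summarised at the other visits, so one derivation error would reach several tables.

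The sign also matters for reading the co-primary result. The success rule in section 8.1.4 asks for statistical significance and names no direction of benefit. With the formula and the label pointing opposite ways, the documents do not fix whether a positive or a negative group difference in %TBWL favours the device.

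**Working it through.** **Inputs.** Mean loss 6% (Treatment) and 3.5% (Control), SD 5, 80% power, 30% dropout and 80 per group, all from section 8.2. The test's alpha is not stated. I assume 0.05 two-sided, in line with the two-sided 95% intervals in section 8.1.1. Normality is also my assumption.

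**The plan's own figure.** The difference is 6 - 3.5 = 2.5.

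n per group = 2 x (1.960 + 0.842)^2 x 5^2 / 2.5^2 = 62.8, so 63.

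Multiplying by 1.3 for dropout gives 82, within two of the stated 80. (Dividing by 0.7 gives 90; that is a separate matter.) The plan's figure is therefore consistent with these means, entered as positive losses. Because the difference enters squared, the sample size is the same under either sign.

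**Sign of the formula.**

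- 90 kg to 84 kg: 100 x (84 - 90)/90 = -6.7, which fails >5%.
- 90 kg to 95.4 kg: 100 x (95.4 - 90)/90 = +6.0, which passes >5%.

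On this scale the planning means would be -6 and -3.5.

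**Responder share, loss counted as positive.**

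- Treatment: P(Z > (5 - 6)/5) = P(Z > -0.2) = 57.9%
- Control: P(Z > (5 - 3.5)/5) = P(Z > 0.3) = 38.2%

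**Responder share, >5 applied to the formula as it stands.**

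- Treatment: P(Z > (5 + 6)/5) = P(Z > 2.2) = 1.4%
- Control: P(Z > (5 + 3.5)/5) = P(Z > 1.7) = 4.5%

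Out of 80 per group, that is about 46 against 31 under the intended rule, and about 1 against 4 under the mechanical one. The difference moves from +19.7 percentage points to -3.1.

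**Sensitivity to the SD (Treatment vs Control).**

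| SD | Loss above 5% | Formula value above 5 |
|---|---|---|
| 3 | 63.1% vs 30.9% | 0.01% vs 0.23% |
| 4 | 59.9% vs 35.4% | 0.30% vs 1.68% |
| 5 | 57.9% vs 38.2% | 1.39% vs 4.46% |
| 6 | 56.6% vs 40.1% | 3.34% vs 7.83% |

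The direction is reversed at every SD.

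**Effect on the co-primary test.** I simulated one data set from the planning values (56 per arm, which is 80 less 30%) and fitted an ANCOVA with baseline weight as covariate, because %TBWL at baseline is zero for everyone. I then changed the sign of the outcome. The treatment estimate went from +2.66 to -2.66, and the two-sided p-value stayed at 0.0016.

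**The case against.** The strongest reply is that the responder endpoint is defined in words. The Protocol Summary and section 6.1.3 count subjects with more than 5% weight loss, and someone who gained 6% has not lost weight. Section 8.1.4 uses the abbreviation TBWL, which the documents expand as total body weight loss, and section 8.2 uses it for losses stated as positive numbers. A reader might infer that the endpoint counts weight gainers as responders. The documents do not support that: gainers enter only if someone applies the signed formula and sets aside the word loss. This part of the reply stands.

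A reader might also infer that the main test is compromised. It is not, provided the test is two-sided, because reversing the sign of the outcome leaves the p-value unchanged.

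It can also be said that the formula is an ordinary percent-change expression, built like the appetite formula in section 8.1.4 (three-month score minus baseline, over baseline). That is fair, and it locates the error: a change formula has been attached to a loss label. It does not remove the mismatch. The >5% cut-off and the formula cannot both be applied as they stand, and nothing in the plan says which gives way.

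**Conclusion.** The point holds as a definition error in a co-primary endpoint that carries into a secondary one. The formula in the Protocol Summary and section 6.1.2 has the opposite sign to the label, the responder cut-off and the planning values. The intended meaning is not in doubt.

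The sample size is unaffected. So is the co-primary p-value if the test is two-sided, which the plan suggests through its intervals but does not state. Only the sign of the reported difference would change. The 1.4% against 4.5% describes what a literal derivation would produce under the plan's means and SD with normality; it is not the endpoint's expected result. The correction is still worth making, because a prespecified endpoint should be programmable from its text without a silent change of sign.

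**What to change.** In the Protocol Summary (Study Endpoints) and section 6.1.2, define %TBWL = 100 x (Initial Weight - End Weight) / Initial Weight. State that positive values mean loss and that a larger value in Treatment favours the device. The >5% cut-off and the 3.5% and 6% planning values then agree without further change.

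In the SAP text of the Summary and in section 8.1.4, also align the sentence introducing the weight ANCOVA. It describes a change from baseline in %TBWL, which is itself already a change from baseline.

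An equally valid route is to keep the formula, call it percent weight change, and set the responder rule at < -5% wherever it appears (Summary endpoints, section 6.1.3, the SAP text and section 8.1.4). This takes more edits.

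The cost of the first route is one line in two places and one sentence in two more. Data collection, the statistical test and the sample size stay as they are.
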